**Which Committee will review this protocol?**

- The Clinical Research Committee - (CRC)

## **1. OBJECTIVES**

### **1.1 Primary Objective**

The primary objective of this study is to evaluate the efficacy of eltrombopag in combination with decitabine for the front-line treatment of Intermediate-2 or High-Risk Myelodysplastic Syndrome (MDS). The primary endpoint is the overall response rate (ORR) based on the IWG-2006 criteria, which includes complete remission (CR), partial remission (PR), and hematologic improvement (HI).

### **1.2 Secondary Objectives**

The secondary objectives of the study are:

- To evaluate the safety and tolerability of the combination of eltrombopag and decitabine. Safety will be assessed by the overall incidence and severity of all study-treatment related adverse events per CTCAE v 4.0
- To evaluate the incidence of dose reductions and delays of decitabine therapy
- To evaluate the effect of eltrombopag on medically significant hemorrhagic events (defined as Grade 3 or 4 hemorrhagic events on CTCAE v 4.0)
- To evaluate the effect of eltrombopag on platelet and RBC transfusion independence per IWG-2006 criteria
- Incidence of transformation to AML per FAB criteria (>30% blasts) during treatment period and follow-up
- Incidence and severity of bone marrow fibrosis during treatment period and follow-up
- To examine the relationship between clinical response with ferritin level and other markers of iron burden at study start

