#### **6.2.2. Primary Safety Endpoint and Safety Considerations**

Primary safety endpoint: The overall incidence and severity of all adverse events including clinically significant thrombocytopenic events using Common Toxicity Criteria v 4.0.

An adverse event is any untoward medical occurrence that may present during treatment with a pharmaceutical product but which does not necessarily have a causal relationship with this treatment. Adverse events (AEs) will be collected using the Leukemia AE guidelines.

Adverse drug reaction is a response to a drug which is noxious and unintended and which occurs at doses normally used in man for prophylaxis, diagnosis, or therapy of disease or for the modification of physiologic function.

All “suspected adverse reactions” (as defined in 21 CFR 312.32(a)) will be captured in the case report forms. For abnormal chemical values grade 3 or 4, the apogee will be reported per course in the CRF.

Assessing causal connections between agents and disease is fundamental to the understanding of adverse drug reactions. In general, a drug may be considered a contributory cause of an adverse event if, had the drug not been administered, 1) the event would not have happened at all, 2) the event would have occurred later than it actually did, or 3) the event would have been less severe.

The Investigator or physician designee is responsible for verifying and providing source documentation for all adverse events and assigning the attribution for each event for all subjects enrolled on the trial. Protocol specific data and adverse events will be entered into PDMS/CORE, the electronic case report form for this protocol.

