#### **6.2.3. Secondary Efficacy Endpoints**

The key secondary endpoints for this study are:

- To evaluate the safety and tolerability of the combination of eltrombopag and decitabine. Safety will be assessed by the overall incidence and severity of all study-treatment related adverse events per CTCAE v 4.0
- To evaluate the incidence of dose reductions and delays of decitabine therapy
- To evaluate the effect of eltrombopag on medically significant hemorrhagic events (defined as Grade 3 or 4 hemorrhagic events on CTCAE v 4.0)
- To evaluate the effect of eltrombopag on platelet and RBC transfusion independence per IWG-2006 criteria
  - o Platelet IWG-2006: A complete response is defined as a platelet count  $> 100 \times 10^9/L$ ; and a major response defined as an increase of platelet count by higher than  $30 \times 10^9/L$ .
  - o Durable platelet count: in which a hematologic improvement in platelets (HI-P) defined as either an increase  $\geq 30 \times 10^9/L$  from patients with a baseline platelet count  $\geq 20 \times 10^9/L$ , or an increase from  $< 20 \times 10^9/L$  to  $\geq 20 \times 10^9/L$  and by at least 100%, present for  $\geq 8$  weeks.
- Incidence of transformation to AML per FAB criteria ( $>30\%$  blasts) during treatment period and follow-up
- Incidence and severity of bone marrow fibrosis during treatment period and follow-up
- To examine the relationship between clinical response with ferritin level and other markers of iron burden at study start

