## 8.4. Safety Endpoints

The incidence of adverse events will be summarized by system organ class and by preferred term according to the MedDRA dictionary for each treatment group. This summary includes all treatment-emergent adverse events recorded from the start of investigational product on this study, or any worsening of adverse events initially experienced before initiation of this study.

Narratives of “on-study” deaths, serious and significant adverse events, including early withdrawals due to adverse events, may also be provided.

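### Safety means treatment-related AEs in 1.2 and 6.2.3 but all AEs in 6.2.2 and 8.4, and 6.2.3 lists safety, hemorrhage and fibrosis as efficacy endpoints, so neither the event definition nor the denominator is settled

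*Combined protocol and SAP*

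**What the plan says.** All references are to the combined protocol and SAP.

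**Which events count.** The secondary objectives (1.2) state: "Safety will be assessed by the overall incidence and severity of all study-treatment related adverse events per CTCAE v 4.0". Section 6.2.3 repeats the restriction: "overall incidence and severity of all study-treatment related adverse events per CTCAE v 4.0". Section 6.2.2 drops it: "Primary safety endpoint: The overall incidence and severity of all adverse events including clinically significant thrombocytopenic events". The same section defines an adverse event as one "which does not necessarily have a causal relationship with this treatment". Section 8.4 describes the planned table: "This summary includes all treatment-emergent adverse events recorded from the start of investigational product on this study". It adds worsening of earlier events and applies no attribution filter.

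**Which patients count.** Section 6.2.3 is headed "Secondary Efficacy Endpoints". Its list includes safety and tolerability, Grade 3 or 4 hemorrhage, and the incidence and severity of marrow fibrosis. Section 6.3.2 analyses efficacy endpoints in enrolled subjects with at least one 28-day cycle of investigational product. Section 6.3.3 analyses safety endpoints in subjects with at least one dose. Section 4.1.1 puts everyone with at least one dose into both analyses. Section 8.1 gives binary secondary endpoints, hemorrhage among them, an exact 95% interval but names no analysis set.

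**Which events are recorded.** Section 6.2.2 has all suspected adverse reactions captured in the case report forms. Section 6.2.2.1 limits CRF entry to unexpected AEs.

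**The concern.** The safety objective and the planned safety table measure different things. Section 1.2 lists safety only as a secondary objective and only through related events, yet no related-only table is planned: 8.4 is all-cause, and the secondary endpoint lists in 8.1 and 8.3 do not mention AEs. An analyst could report either rate and cite the protocol for it.

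The choice has weight here because attribution is hard. Section 2.1 describes cytopenias as part of MDS and myelosuppression as common on decitabine. In an open-label, single-arm study, the split between related and unrelated events rests on investigator judgement with no comparator.

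The denominator is a second open question. If the heading of 6.2.3 is applied literally with 6.3.2, a patient who bleeds and leaves during cycle 1 is absent from the hemorrhage rate. Section 2.2 names hemorrhage and platelet transfusion as the consequences on which clinical benefit rests, so this estimate should not depend on a section title.

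**Working it through.** The plan gives no AE or hemorrhage figure to reproduce. The check sets the sections side by side, then uses assumed counts to show the possible size.

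**Step 1. The text.**

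| Section | Events | Analysis set |
|---|---|---|
| 1.2 | Treatment-related | Not stated |
| 6.2.2 | All, causality not required | Safety by name, so 6.3.3 |
| 6.2.3 | Treatment-related; hemorrhage and fibrosis listed separately | Efficacy by heading, so 6.3.2 |
| 8.1 | Hemorrhage and fibrosis | Not stated |
| 8.4 | All treatment-emergent | Safety by heading, so 6.3.3 |

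No section ranks these. Hemorrhage is Grade 3 or 4 in 1.2, 6.2.3 and 8.1, with no relatedness condition in any of them. Its rate can therefore change only through the analysis set.

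**Step 2. Effect of the event definition.** In the same N patients over the same period, patients with a related event (R) are a subset of patients with any event (A). So R/N ≤ A/N always. With N = 40 (Section 8) and an assumed A = 28, using the exact intervals named in 8.1:

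- All-cause: 28/40 = 70.0% (53.5 to 83.4%)
- 25% of these patients have a related event: 7/40 = 17.5% (7.3 to 32.8%)
- 50%: 14/40 = 35.0% (20.6 to 51.7%)
- 75%: 21/40 = 52.5% (36.1 to 68.5%)

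**Step 3. Effect of the analysis set on hemorrhage.** Let x patients bleed among N treated, d leave before completing cycle 1, and h of the x be among those d. The safety-set rate is x/N and the efficacy-set rate is (x − h)/(N − d). The efficacy-set rate is lower only when h/d > x/N, that is, when early leavers bled more often than treated patients overall. With assumed x = 4 and N = 40, the safety-set rate is 4/40 = 10.0% (2.8 to 23.7%). The efficacy-set rates are:

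| d | h = 0 | h = 1 | h = 2 |
|---|---|---|---|
| 2 | 4/38 = 10.5% | 3/38 = 7.9% | 2/38 = 5.3% |
| 4 | 4/36 = 11.1% | 3/36 = 8.3% | 2/36 = 5.6% |
| 6 | 4/34 = 11.8% | 3/34 = 8.8% | 2/34 = 5.9% |

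The extremes are 2/38 (exact interval 0.6 to 17.7%) and 4/34 (3.3 to 27.5%).

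**Step 4. Stopping rules.** Section 8 monitors a toxicity outcome with its own definition. Exact enumeration reproduces every Table 3 boundary (4, 6, 8, 9, 11, 13, 15) and the Table 4 stopping probabilities to within 0.002. Tables 1 and 2 concern response. None of the four uses the definitions at issue here.

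**The case against.** The strongest reply is that the all-event analysis is already planned. Section 6.2.2 names all AEs as the primary safety endpoint, 8.4 tabulates them without a filter, and 6.2.2 requires attribution for each event, so a related subset could be added. On that view, 6.2.2 and 1.2/6.2.3 describe two tables, and the title of 6.2.3 is a labelling slip: its lead-in speaks only of key secondary endpoints, and its first item calls itself safety and tolerability. Much of this stands. A reader might infer that events put down to MDS vanish from the report; under 8.4 they do not. What remains is that no section states the two-table hierarchy or plans the related-only table.

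Section 4.1.1 is also a real counterweight. Under it, a patient who bleeds and leaves in cycle 1 is counted even if hemorrhage is called efficacy. Exclusion is thus one literal reading, not a certain consequence. But 4.1.1 conflicts with 6.3.2 and does not settle the matter.

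Three stronger readings should not be drawn:

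- That attribution would shrink the hemorrhage rate. The hemorrhage endpoint has no relatedness filter.
- That the safety rates as a whole are biased low. This follows for a related-only AE rate, but Step 3 shows the analysis-set effect has no fixed direction.
- That 4.1 proves the losses fall where risk is highest. It refers to the initial cycles in general, whereas 6.3.2 removes only patients without one full cycle.

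Finally, these are descriptive outputs, and no sample size, decision rule or primary result depends on them. That limits the severity but does not remove the ambiguity.

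**Conclusion.** The inconsistency is real and should be resolved. Two AE definitions stand without a governing rule. A literal reading of 6.2.3 with 6.3.2 can exclude early events from safety, hemorrhage and fibrosis, while 4.1.1 and 6.3.3 point to the at-least-one-dose set.

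The related-only AE rate equals or understates the all-cause rate; on the assumed 28 of 40, it is 17.5% to 52.5% against 70.0%. For hemorrhage, the set chosen moves an assumed 10.0% to between 5.3% and 11.8%. These figures rest on assumed event counts, early departures and related shares; the documents supply only N = 40 and the interval method. With so few events the exact intervals overlap widely, so the point concerns a well-defined estimate, not a demonstrated bias.

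The CRF restriction in 6.2.2.1 may matter more in practice. Taken at its word, it could leave the 8.4 table without the data it needs. The AE guidelines that 6.2.2 invokes for collection are not in the documents, so whether they fill that gap cannot be checked.

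**What to change.** 1. In 1.2, 6.2.2, 6.2.3 and 8.4, state one primary safety measure: incidence and worst grade of all treatment-emergent AEs regardless of attribution, in the 6.3.3 set. Add treatment-related AEs as a labelled subset table.
2. Move safety, hemorrhage and fibrosis out of the efficacy list in 6.2.3, and name the 6.3.3 set for them in 8.1. Keep hemorrhage free of any relatedness condition.
3. Reconcile the CRF rule in 6.2.2.1 with 6.2.2 and 8.4, so that expected as well as unexpected AEs are available for the all-event table.

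The first two are wording changes. The third brings some additional AE data entry and is best settled before data accumulate. Reported AE rates may look less favourable than related-only rates. The sample size and Tables 1 to 4 do not change.

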## **2. BACKGROUND AND SCIENTIFIC RATIONALE**

### **2.1 Background**

Myelodysplastic syndromes (MDS) are malignant clonal disorders characterized by ineffective hematopoiesis, bone marrow dysplasia, peripheral cytopenias including thrombocytopenia, and a propensity to transform into acute myeloid leukemia (AML). Classically, MDS is associated with apoptosis and excessive proliferation, resulting in a paradoxical combination of a hyper-cellular marrow and peripheral cytopenias. The incidence of MDS in the United States is rising, with approximately 20,000 to 30,000 new cases of MDS diagnosed annually, and a median age at diagnosis of 70 years.

Over the past decade, clinical use of the hypomethylating agent decitabine has been shown to improve patient quality of life, decrease transfusion requirements, and improve outcome parameters in MDS patients, and is now a standard of care for MDS patients requiring therapy. However, myelosuppression including severe thrombocytopenia is commonly seen in decitabine-treated patients, and is the most frequent cause of dose reduction, delay and discontinuation of the HMA agents (including both decitabine and 5-azacitidine) in up to 80% of patients. With current HMA regimens, achievement of an ORR is estimated at 28-70%, with a CR rate of only 6-34% in patients treated with front-line HMA therapy, and with a median length of response in the HMA-responders of only 8 to 10 months.

As alluded to above, the platelet count in MDS patients is critically important, and impacts both treatment decisions and overall survival in the majority of MDS patients. Among 2410 patients with MDS referred to the MD Anderson Cancer Center, 67% had a platelet count  $<100 \times 10^9/L$  at the time of their initial consultation, with over 10% of patients presenting with life-threatening thrombocytopenia ( $<20 \times 10^9/L$ ). The frequency of hemorrhagic deaths within this population ranged from 14 to 24%.

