## 2.2 Rationale for Use of Eltrombopag and Dose Selection

Eltrombopag (Promacta), a second-generation thrombopoietin-receptor agonist (TPO-RA), is a synthetic small-molecule oral thrombopoietin mimetic that binds to c-MPL,

promoting megakaryopoiesis and release of platelets from mature megakaryocytes. It is currently FDA-approved for the treatment of immune thrombocytopenic purpura (ITP) and hepatitis C (HCV) associated thrombocytopenia. Eltrombopag has a unique mechanism of action compared to the other TPO-RAs, and functions through binding to a transmembrane domain of the TPO-receptor, activating the JAK/STAT pathway but producing much less activation of the STAT family, and without activation of the Akt pathway. Intriguingly, in cell lines and in Phase I clinical studies, eltrombopag has shown anti-leukemia activity unrelated to the TPO-RA pathway, leading to a modest inhibition of leukemia or MDS cell growth, while continuing to simulate normal megakaryopoiesis in bone marrow samples, and has also been associated with multilineage clinical responses in patients with severe and refractory aplastic anemia.

This study will enroll patients with advanced MDS, defined as IPSS Int-2 or high-risk MDS, or IPSS-R high or very-high MDS and with thrombocytopenia with a platelet count < 100K. The study will explore the supportive care and disease-modifying effects of eltrombopag in addition to decitabine standard of care treatment for advanced MDS. In patients with advanced MDS receiving decitabine, the consequences of low platelet counts, namely platelet transfusions and hemorrhage, form the basis of clinical outcomes which provide clinically meaningful benefit.

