## 8. Statistical Considerations

This is an open label, phase II clinical trial to evaluate the efficacy of eltrombopag in combination with decitabine as a frontline therapy in patients with Intermediate-2 or High-Risk Myelodysplastic Syndrome (MDS). A total of 40 patients will be accrued from M.D. Anderson Cancer Center (MDACC), at a rate of 2-3 patients per month.

The primary endpoint is the overall response rate (ORR) based on the IWG-2006 criteria, which includes complete remission (CR), partial remission (PR), and hematologic improvement (HI). Patients' overall response will be assessed during the first four 28-day cycles of treatment. Patients who drop off the study early due to treatment-related toxicities will be counted as treatment failures (i.e., non-responders).

The method of Thall, Simon and Estey [1995] will be used for futility and toxicity monitoring for this study. The target overall response rate is 60% and the following futility stopping rule will be applied in cohort size of 10, starting from the 10th patient:  $\text{prob}\{p(\text{ORR}) < 0.6\} > 0.95$ , where  $p(\text{ORR})$  denotes the overall response rate. That is, the trial will be stopped early due to futility, if during the study we determine that there is more than 95% chance that the ORR is less than 60%. Assuming that the prior distribution of  $p(\text{ORR})$  is beta (1.2, 0.8), the stopping boundaries corresponding to this futility monitoring rule are shown below in Table 1. The operating characteristics (OCs) for this futility stopping rule are summarized in Table 2. The design software Multic Lean Desktop (version 1.2.0) developed by the Department of Biostatistics at M. D. Anderson Cancer Center (MDACC) was used to generate the futility stopping boundaries and the

OC table. In order to utilize the software for the design, a highly informative beta (600, 400) prior was assumed to approximate the target 60% overall response rate.

Table 1. Futility stopping boundaries in cohort size of 10.

Number of patients	Stop the trial if there are this many patients achieving overall response
10	0-3
20	0-8
30	0-13

Table 2. Operating characteristics for futility monitoring in cohort size of 10 (max sample size = 40).

True ORR	Prob(stop the trial early due to futility)	Average sample size
0.3	0.971	14.8
0.4	0.775	22.0
0.5	0.391	31.3
0.6	0.105	37.5
0.7	0.015	39.6

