## 8.1 Analysis Plan

The primary endpoint is overall response rate (ORR). The ORR will be estimated along with the exact 95% confidence interval. Secondary endpoints include incidence of dose reductions and delays of decitabine therapy, hemorrhagic events (defined as Grade 3 or 4 hemorrhagic events on CTCAE v 4.0), platelet and RBC transfusion independence per IWG-2006 criteria, transformation from MDS to AML, Incidence and severity of bone marrow fibrosis. Descriptive statistics will be used to summarize all secondary endpoints. The incidence rates of binary secondary endpoints will be estimated, along with the exact 95% confidence intervals.

The probabilities of time-to-event outcomes (such as time to transformation from MDS to AML and time to developing BM fibrosis) will be estimated using the method of

Kaplan and Meier. Log-rank tests will be used to compare the time-to-event outcomes among subgroups of patients.

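### The severe-hemorrhage endpoint counts only Grade 3 or 4 events, so a patient whose only severe bleed is fatal is left out of the reported rate

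*Combined protocol and SAP*

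**What the plan says.** Section 1.2 lists, among the secondary objectives, the effect of eltrombopag on medically significant bleeding, "defined as Grade 3 or 4 hemorrhagic events on CTCAE v 4.0". Section 6.2.3 repeats the definition among the key secondary endpoints, and section 8.1 repeats it in the analysis plan: "hemorrhagic events (defined as Grade 3 or 4 hemorrhagic events on CTCAE v 4.0"). The three agree. None mentions Grade 5, a fatal event, or an open-ended upper grade, and no other section supplies a counting rule for a bleed that ends in death.

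The planned analysis is descriptive. Section 8.1 states: "The incidence rates of binary secondary endpoints will be estimated, along with the exact 95% confidence intervals". The trial is single-arm with 40 patients (sections 4.1 and 8).

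The rationale gives bleeding real weight. Section 2.2 says the consequences of low platelets, "namely platelet transfusions and hemorrhage, form the basis of clinical outcomes which provide clinically meaningful benefit". Section 2.1 says of a large referral series: "The frequency of hemorrhagic deaths within this population ranged from 14 to 24" per cent.

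**The concern.** The CTCAE is the protocol's adopted grading scale, and on it death from an event has its own grade above 4. The documents do not reproduce the scale, but the seriousness criteria in section 6.2.2.1 likewise list death separately from life-threatening events. A definition limited to Grades 3 and 4 therefore leaves out the worst form of the outcome it is meant to summarise.

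The error runs in one direction. A patient with a life-threatening bleed counts as an event. A patient who dies of a bleed, with no earlier Grade 3 or 4 bleed recorded, does not. What is at stake is the accuracy of one published rate and its interval. If the definition is left alone, analysts must also decide how to treat fatal bleeds after seeing the data.

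**Working it through.** The documents give no expected rate, power or sample-size figure for hemorrhage, so there is no stated figure to reproduce. The check has two parts.

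**1. Does any section bring fatal bleeds into the rate?**

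- Section 4.1: bleeding events are assessed throughout, with no grade limit. This is collection, not the endpoint.
- Section 6.2.2: the primary safety endpoint covers all adverse events and their severity. A fatal bleed belongs here, but in a different summary.
- Section 6.2.2.1: death makes an event serious. This concerns reporting.
- Section 8, toxicity rule: a serious event felt to be drug related counts as toxicity. A fatal bleed attributed to the disease does not enter.
- Sections 6.2.1 and 8.3: overall survival counts death from any cause, without isolating bleeding.
- Section 8.4: narratives of on-study deaths are optional.

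None of these adds a fatal bleed to the hemorrhage incidence in section 8.1.

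**2. How far can the rate move?**

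Let *a* be the number of patients with a recorded Grade 3-4 bleed and *f* the number whose only severe bleed was fatal, with *n* = 40 as denominator (section 8). The rate as written is *a*/40 and the inclusive rate is (*a* + *f*)/40. The shortfall is *f*/40, or 2.5 percentage points per patient, and cannot be negative.

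The exact (Clopper-Pearson) 95% limits for *x* events are the 0.025 quantile of Beta(*x*, *n* − *x* + 1) and the 0.975 quantile of Beta(*x* + 1, *n* − *x*). With *a* = 4, an assumed count:

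| Further fatal bleeds *f* | As written | Grade 3 or higher |
|---|---|---|
| 0 | 4/40 = 10.0% (2.8-23.7%) | 4/40 = 10.0% (2.8-23.7%) |
| 1 | 10.0% (2.8-23.7%) | 5/40 = 12.5% (4.2-26.8%) |
| 2 | 10.0% (2.8-23.7%) | 6/40 = 15.0% (5.7-29.8%) |
| 4 | 10.0% (2.8-23.7%) | 8/40 = 20.0% (9.1-35.6%) |

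The perverse direction shows if one of those four bleeds had instead been fatal from the outset. The rate as written would fall to 3/40 = 7.5% (1.6-20.4%), while the inclusive rate would stay at 10.0%.

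Whether any such patient occurs depends on a risk *p* that the documents do not give: the chance that a patient has a fatal bleed on study and no separately recorded Grade 3-4 bleed. The chance of at least one in 40 is 1 − (1 − *p*)^40. For assumed values of *p*:

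- 1%: 33%, expected number 0.4
- 2.5%: 64%, expected number 1
- 5%: 87%, expected number 2

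**The case against.** The strongest reply is that fatal bleeding is not lost. It should be collected as a bleeding event and as a serious event, it falls under the all-adverse-event safety endpoint and overall survival, and it reaches the toxicity rule if judged drug related. That stands. A reader might infer from the definition that fatal bleeding would go unseen in this trial, and the documents do not support that. They support only that one summary rate can omit it. The other capture is uneven, since section 6.2.2.1 also limits case report form entry to unexpected adverse events.

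Second, the loss is conditional. A patient with a recorded Grade 3 or 4 bleed who later dies of bleeding is already counted, and the number affected could be zero. This also stands.

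Third, the grade wording may be loose shorthand for severe events rather than a decision to exclude deaths. That is possible, and nothing in the documents shows intent. But with the same wording in three places and no counting rule, the literal reading is the one an analyst would have to follow or knowingly depart from.

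Fourth, a reader might apply the 14-24% of section 2.1 to 40 patients and expect about 6 to 10 fatal bleeds (0.14 × 40 = 5.6; 0.24 × 40 = 9.6). The documents do not support this. The figure has no stated time window, its denominator is unclear, and trial observation is bounded by treatment and follow-up. It shows that fatal bleeding matters in this disease, not how often it will occur here.

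**Conclusion.** The point holds as a defect in one secondary endpoint. As defined, it does not count a patient whose only severe bleed is fatal, and its incidence and exact interval can be biased downward by 2.5 percentage points per such patient. The conclusion rests on the literal definition and on death being graded above 4 on the adopted scale. The 10.0% to 20.0% illustration rests wholly on assumed counts and is not a forecast, and its intervals overlap widely.

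The consequences are limited. The endpoint is descriptive, with no hypothesis, error rate or boundary attached. The overall response rate analysis and both sets of stopping boundaries are unaffected. A reader might also infer that the corrected rate would show whether eltrombopag causes or prevents bleeding. It would not: with a single arm and no comparator, the rate describes what happened to these patients and cannot by itself establish an effect.

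**What to change.** In sections 1.2, 6.2.3 and 8.1, define the endpoint as Grade 3 or higher (including fatal) hemorrhagic events. State in section 8.1 that each patient is counted once at worst grade, and report fatal hemorrhage on a separate line beside the combined rate and its exact 95% interval.

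This is a wording change in three places plus one line in a table. It needs no extra patients, visits or tests and touches no treatment rule. The one downside is that the reported rate may be less favourable. It would help at the same time to reconcile the case report form limit in section 6.2.2.1 with the continual bleeding assessment in section 4.1, so that expected bleeds of every grade reach the database.
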